5.4.1. CYP3A and UGT Inhibitors

Although pexidartinib does not appear to inhibit cytochrome P450 (CYP) drug-metabolizing enzymes to an important extent, caution is warranted when administering pexidartinib to subjects taking drugs that are highly dependent on CYP for metabolism and have a narrow therapeutic index. It is not known whether systemic exposure to these medications will increase while subjects are receiving pexidartinib.

Of the five major CYP isoforms, 3A4 (BFC) may be involved in Phase 1 metabolism of pexidartinib, with possibly CYP1A2 playing a minor role (see Section 15.1 for a list of common CYP3A4 inhibitors and inducers). In general, strong inducers of CYP3A4 should be avoided unless clinically necessary. These include anticonvulsants, certain mycin antimicrobials, and antiretrovirals. Some common examples include inducers such as rifampicin, carbamazepine, phenytoin, efavirenz, and nevirapine.²¹

Avoid concomitant use of pexidartinib with moderate or strong CYP3A inhibitors or UGT inhibitors. If concomitant use with a moderate or strong CYP3A inhibitor or UGT inhibitor cannot be avoided, reduce the pexidartinib dose according to the recommendations in Table 5.3. If concomitant use of a moderate or strong CYP3A inhibitor or UGT inhibitor is discontinued, increase the pexidartinib dose (after 3 plasma half-lives of the moderate or strong CYP3A inhibitor or UGT inhibitor) to the dose that was used before starting the inhibitor.

Table 5.3: Recommended Dosage Reductions for Pexidartinib with Concomitant Use of Moderate or Strong CYP3A Inhibitors or UGT Inhibitors

Current Total Daily Dose	Modified Total Daily Dose	Administration of Modified Total Daily Dose
800 mg	400 mg	200 mg twice daily
600 mg	400 mg	200 mg twice daily
400 mg	200 mg	200 mg once daily

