1.4. Study Rationale

This study will be conducted in two parts. Part 1 will be a double-blind randomized placebo-controlled Phase 3 trial in subjects with symptomatic PVNS or GCT-TS for whom surgical resection would be associated with potentially worsening functional limitation or severe morbidity (locally advanced disease). Eligible candidates will be randomized in a 1:1 ratio to receive either pexidartinib or placebo twice daily for 24 weeks. The double-blind and randomized design will allow adequate comparison of pexidartinib with a control group. Placebo was selected as the control group because there is no existing non-surgical treatment that is accepted as standard of care for PVNS/GCT-TS. Surgical treatment cannot be used as a control treatment because the patient population includes those for whom surgery is associated with

potentially worsening function limitation or severe morbidity. Both the placebo and pexidartinib treatment groups will receive the usual supportive standard of care, eg, analgesic medications.

Subjects will be started with 1000 mg/d pexidartinib or matching placebo, ie five capsules, in Part 1. It will be split into a morning dose of two capsules (400 mg pexidartinib or matching placebo) and an evening dose of three capsules (600 mg pexidartinib or matching placebo) and will be given in the fasting state (no food for 1 hour before and 2 hours after dosing, with a low-fat snack if needed). Beginning on P1-C1D15, the maximum daily dose will be reduced to four capsules (800 mg pexidartinib or matching placebo) if it has not already been reduced to that amount or less. When subjects begin Part 2, they will continue taking the same number of capsules but of open-label pexidartinib, also split into a morning and an evening dose. Selection of the pexidartinib starting dose of 1000 mg/d and the split-dose administration schedule is based on data from subjects with solid tumors, including the small cohort of subjects with PVNS who received pexidartinib in Study PLX108-01, a Phase 1 trial. In the dose-escalation portion of that trial, two subjects receiving 1200 mg/d, administered as a split dose, experienced dose-limiting toxicities: anemia, neutropenia, and syncope in one subject and elevated AST in the other. For this reason, 1000 mg/d given as a split dose was selected as the maximum tolerated dose and the recommended Phase 2 dose.

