5.2. Study Treatment Administration

Study treatment will only be given to randomized subjects under the supervision of the Principal Investigator or identified sub-Investigator(s). The study treatment for home administration during Part 1 will be dispensed to the subject for the first time at the P1-C1D1 visit (within 3 days of randomization), and the study treatment for home administration during Part 2 will be dispensed to the subject for the first time at the P2-C1D1 visit. Capsules should be swallowed and not crushed, chewed, or dissolved in liquid. In Part 1, subjects will receive either pexidartinib or matching placebo capsules. In Part 2, subjects will receive only pexidartinib capsules.

Study treatment administration will begin at the P1-C1D1 visit in the morning. At that visit, subjects will be instructed to take five capsules a day for the first 2 weeks; 1000 mg/d pexidartinib or matching placebo, this amount will be divided into a morning dose of two capsules and an evening dose of three capsules. After 2 weeks (at the P1-C1D15 visit), the dose will be reduced to two capsules in the morning and two capsules in the evening, 800 mg/d pexidartinib or matching placebo. Subjects who had a dose reduction during the first 2 weeks will continue treatment at their reduced dose. Doses should be taken in the fasting state (ie, no food for 1 hour before and 2 hours after dose administration). During the fasting period, subjects will be permitted to eat a low-fat snack (eg, crackers, toast, tea) if needed. Doses will be taken at approximately the same times of the day and approximately 12 hours apart. Each dosing cycle will be 28 days.

For the P1-C1D15 and P2-C1D15 visits and any visit when an ECG will be performed, subjects should be told to NOT take their morning dose of study treatment before coming to their study visit, which should be scheduled for the morning; instead, they should be told to bring their bottle of study treatment to the clinic and take their morning dose upon instruction by the study site. The time of dosing will be recorded. Subjects will then take their evening dose at home. If dose administered in the clinic is taken in the afternoon, then the subject should be instructed to skip their evening dose for that day.

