5.3. Dose Modification Guidelines

In both Parts 1 and 2, reducing or interrupting the dose for toxicity may take place at any time according to the guidelines in [Table 5.1](#) and [Table 5.2](#). Dose reduction/interruption guidelines for hematologic and non-hematologic treatment-related TEAEs are based on severity. Dose interruptions can be implemented at the discretion of the treating physician to manage intolerable or clinically significant toxicity. If a dose interruption is required, study assessments should be performed as scheduled, irrespective of the study treatment delay, with the exception of PK assessments which should be deferred until treatment is resumed. Interruptions due to toxicity lasting >14 d require treatment discontinuation unless the medical monitor approves continuation.

When an odd number of capsules a day are to be taken, the larger number of capsules should be taken as the evening dose. For example, 600 mg/d or matching placebo = 3 capsules (1 capsule in the morning, 2 capsules in the evening). When an even number of capsules per day is to be taken, the morning and evening doses should be the same (eg, 800 mg/d or matching placebo = 4 capsules (2 capsules in the morning, 2 capsules in the evening) or 400 mg/d or matching placebo = 2 capsules (1 capsule in the morning, 1 capsule in the evening).

Dose reductions should be applied in increments of 200 mg/d or matching placebo (one capsule), with a maximum total reduction of 600 mg/d or matching placebo (ie, a minimum dose of 400 mg/d or matching placebo). Subjects unable to tolerate 400 mg/d or matching placebo (two capsules) will be discontinued. Once dose reduction takes place for toxicity, a dose re-escalation is generally not allowed unless approved after discussion with the Sponsor's Medical Monitor or designee.

Dose-modification guidelines for treatment-emergent toxicities as well as guidelines for their management are presented [Table 5.1](#) and [Table 5.2](#). These parameters are only a guide and are not intended to supersede the clinical judgment of the treating physician. All adjustments should be communicated to the Sponsor's Medical Monitor or designee. Rechallenge with a reduced dose of pexidartinib may result in a recurrence of increased serum transaminases, bilirubin, or ALP. Monitor liver tests weekly for the first month after rechallenge.

Table 5.1: Dose Modification Guidelines for Treatment-emergent Toxicities

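### When toxicity occurs during use of a CYP3A or UGT inhibitor, the dose instructions in Sections 5.3 and 5.4.1 cannot all be followed and need to be reconciled

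*Combined protocol and SAP*

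**What the plan says.** Section 5.3 covers both Parts. On step size it says "Dose reductions should be applied in increments of 200 mg/d or matching placebo (one capsule"), and it bounds the reductions "with a maximum total reduction of 600 mg/d or matching placebo (ie, a minimum dose of 400 mg/d or matching placebo"). Subjects who cannot tolerate 400 mg/d are discontinued. On going back up it says "Once dose reduction takes place for toxicity, a dose re-escalation is generally not allowed unless approved after discussion" with the Medical Monitor or designee. Table 5.1 directs that drug withheld for raised transaminases, for raised bilirubin in the lower band, or for other severe or intolerable events is restarted at a reduced dose if the recovery conditions are met.

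Section 5.4.1 deals with moderate or strong CYP3A inhibitors and UGT inhibitors. These are to be avoided. If that is not possible, Table 5.3 takes 800 mg/d to 400, 600 to 400, and 400 to "200 mg once daily". When the inhibitor is discontinued and three of its half-lives have passed, the dose is increased "to the dose that was used before starting the inhibitor".

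Section 5.4.1 does not mention toxicity reductions or the 400 mg/d minimum. Section 5.3 does not mention inhibitor-driven reductions. Neither refers to the other on these points.

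**The concern.** Two sets of dose rules can apply to the same subject at the same time, and the protocol does not say how they combine. The sequence that matters is toxicity that begins while the inhibitor is being taken. A site then has to decide what counts as a reduced dose, whether the stated minimum blocks it, and what to give if the inhibitor is stopped during the hold.

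The stakes are mainly safety. The December 2017 hepatic safety update that follows Section 1.5 describes severe and fatal liver injury, and Section 5.3 warns that transaminase, bilirubin or ALP rises may recur on rechallenge even at a reduced dose. There is also a data consequence. Sites that resolve the ambiguity differently will produce different discontinuations and different exposures, and individual exposures feed the exposure-response work in Section 7.9.

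**Working it through.** **Inputs.** Starting dose 1000 mg/d, from Section 5.2: "subjects will be instructed to take five capsules a day for the first 2 weeks; 1000 mg/d pexidartinib or matching placebo". Step 200 mg/d, maximum total reduction 600 mg/d and minimum 400 mg/d, from Section 5.3. Dose pairs 800→400, 600→400 and 400→200 mg/d, from Table 5.3.

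**The plan's own figure.** 1000 − 600 = 400 mg/d. The stated minimum reproduces from the Part 1 starting dose.

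**Table 5.3 against the minimum.** Two rows end at 400 mg/d, at the minimum. The third ends at 200 mg/d, which is 400 − 200 = 200 mg/d below it. Its total reduction from the start is 1000 − 200 = 800 mg/d, against a stated maximum of 600.

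**Toxicity while on the inhibitor.** Table 5.1 says to restart at a reduced dose but not what the reduction is counted from. There are two possible readings, each with a one-capsule step:

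| Pre-inhibitor dose (mg/d) | Table 5.3 dose | Reading A: one capsule off the Table 5.3 dose | Reading B: one capsule off the pre-inhibitor dose, then Table 5.3 | Section 5.4.1 dose once inhibitor stops | Rise from Table 5.3 dose |
|---|---|---|---|---|---|
| 800 | 400 | 400 − 200 = 200 | 600, then 400 | 800 | 800 − 400 = 400 |
| 600 | 400 | 400 − 200 = 200 | 400, then 200 | 600 | 600 − 400 = 200 |
| 400 | 200 | 200 − 200 = 0 | 200, no row in Table 5.3 | 400 | 400 − 200 = 200 |

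Under reading A, no row leaves a reduced dose at or above 400 mg/d. Under reading B, the first row restarts at the same 400 mg/d on which the toxicity arose, and the other two fall below 400. Neither reading satisfies Table 5.1, Table 5.3 and the minimum together with an actual drop in dose.

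**Inhibitor stopped during the hold.** Section 5.4.1, read literally, gives the pre-inhibitor dose in full: 800, 600 or 400 mg/d. Table 5.1 gives a reduced dose. The re-escalation limit in Section 5.3 bears on the same decision if a reduced dose has already been started, and the hepatic safety update asks for discussion with the Medical Monitor before any rechallenge. No sentence says which instruction prevails.

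**Toxicity reduction before the inhibitor.** Take 800 → 600 for toxicity, 600 → 400 with the inhibitor, then back to 600. The pre-inhibitor dose is already the reduced one, so nothing is reversed and the rules agree.

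**The 600 and 400 mg/d figures in Part 2.** Subjects who had placebo in Part 1 and entered Part 2 before 30 Sep 2016 started pexidartinib at no more than 800 mg/d. From there 800 − 600 = 200 mg/d, not 400.

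**The case against.** The strongest reply is that the two sections differ in scope. Section 5.3 opens by saying that "reducing or interrupting the dose for toxicity may take place at any time according to the guidelines in" its two tables, its discontinuation rule turns on tolerance, and it calls its parameters a guide that does not override clinical judgment. Table 5.3 concerns drug interaction and is headed as a recommendation. On that view the 200 mg/d row is a separate matter. This is a reasonable reading and softens the clash over the minimum, but the protocol does not state it. The sentence that sets the step and the minimum, unlike the re-escalation sentence, is not limited to toxicity. Scope also does not help the subject to whom both sets of rules apply.

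Several stronger readings are tempting, and the documents do not support them.

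- A reader might infer that Section 5.4.1 reverses any toxicity reduction. No passage says so, and it does not happen when the reduction preceded the inhibitor. The re-escalation limit also starts only once a dose has been reduced for toxicity, and it allows approved exceptions.
- A reader might infer that the dose could be raised after liver injury with no medical review. Section 5.3 asks that all adjustments be communicated to the Medical Monitor, Table 5.2 asks for consultation before restart and discussion of every liver-related hold, and the hepatic safety update asks for discussion before rechallenge.
- A reader might infer that an inhibitor started in the first two weeks could bring back 1000 mg/d, since Table 5.3 has no row for it. Section 1.4 says that from P1-C1D15 "the maximum daily dose will be reduced to four capsules", and Sections 3.1 and 5.2 keep subjects reduced earlier at their reduced dose.
- A reader might call the 600 mg/d figure an error. It is correct from the 1000 mg/d start, and the 400 mg/d minimum beside it is clear.

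**Conclusion.** The point holds for toxicity that arises during inhibitor use. One of three Table 5.3 rows lies below the stated minimum. None of the three leaves a one-capsule reduction from the inhibitor-adjusted dose that respects that minimum. If the inhibitor stops during a hold, Section 5.4.1 and Table 5.1 give different instructions, with Section 5.4.1 pointing to 200 or 400 mg/d above the dose on which the toxicity occurred. This goes beyond missing detail, because Section 5.4.1 followed to the letter can restore the full earlier dose after a liver-test hold. The mismatch between 600 and 400 mg/d is minor and is confined to subjects whose pexidartinib began at 800 mg/d in Part 2.

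The conclusion assumes one-capsule steps, as in Section 5.3, and that the minimum means what it says in the absence of a stated exception. The number of subjects affected cannot be estimated, since the documents do not say how many take such inhibitors and ask that they be avoided. No effect on discontinuation counts or on the exposure-response results has been shown. The case for acting rests on safety and on giving every site the same instruction.

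**What to change.** The sponsor should reconcile Section 5.3, Table 5.1, Section 5.4.1 and Table 5.3 so that a single instruction covers each of these:

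1. What applies when study drug is withheld or reduced for toxicity during inhibitor use and the inhibitor is then stopped.
2. Whether a toxicity reduction on an inhibitor is counted from the inhibitor-adjusted dose or from the underlying dose.
3. Whether the 400 mg/d minimum, and the discontinuation rule tied to it, cover inhibitor-driven reductions.
4. How the 600 mg/d maximum reduction and the 400 mg/d minimum are to agree in both Parts.

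Which dose or rule prevails is for the sponsor to decide, and none is proposed here. The cost is a few sentences and cross-references in Sections 5.3 and 5.4.1 and a note to Table 5.3. No new assessments or subjects are needed.

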5.4.2. Hormonal Contraceptives

Pexidartinib has been indicated to be a moderate CYP3A4 inducer, as concurrent administration of pexidartinib decreased the AUC_{inf} of the CYP3A4 substrate midazolam by 57%. As the hormonal contraceptive ethinyl estradiol is a CYP3A4 substrate, there is a potential that exposure of ethinyl estradiol may decrease on concurrent administration with pexidartinib. As pexidartinib may cause embryo-fetal harm when administered to a pregnant woman, females of reproductive potential should be advised to use an effective, non-hormonal method of contraception during treatment with pexidartinib and for 1 month after the last dose. Males with female partners of reproductive potential should be advised to use an effective method of contraception during treatment with pexidartinib and for 1 month after the last dose. Female partners of male patients should concurrently use effective contraceptive methods (hormonal or non-hormonal).

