
Inclusion Criteria
	
 1. Age \geq 18 years. 2. A diagnosis of PVNS or GCT-TS (i) that has been histologically confirmed either by a pathologist at the treating institution or a central pathologist, and (ii) where surgical resection would be associated with potentially worsening functional limitation or severe morbidity (locally advanced disease), with morbidity determined consensually by qualified personnel (eg, two surgeons or a multi-disciplinary tumor board). 3. Measurable disease as defined by RECIST 1.1 (except that a minimal size of 2 cm is required), assessed from MRI scans by a central radiologist. 4. Symptomatic disease because of active PVNS or GCT-TS, defined as one or more of the following: 
 a. a worst pain of at least 4 at any time during the week preceding the Screening Visit (based on scale of 0 to 10, with 10 representing “pain as bad as you can imagine”). b. a worst stiffness of at least 4 at any time during the week preceding the Screening Visit (based on a scale of 0 to 10, with 10 representing “stiffness as bad as you can imagine”). 5. Stable prescription of analgesic regimen during the 2 weeks prior to randomization. 6. During the 2 weeks prior to randomization, at least 4 of 7 consecutive days of BPI Worst Pain NRS items and Worst Stiffness NRS items completed correctly. 7. Women of childbearing potential must have a negative serum pregnancy test within the 14-day period prior to randomization. (Where demanded by local regulations, this test may be required within 72 hours of randomization.) 8. Males and females of childbearing potential are permitted in the study so long as they consent to avoid getting their partner pregnant or becoming pregnant, respectively, by using a highly effective contraception method, as described below, throughout the study and for up to 90 days after completion. Highly effective methods of contraception include: intra-uterine device (nonhormonal or hormonal), bilateral tubal occlusion, vasectomy, sexual abstinence, or barrier methods (e.g., condom, diaphragm) used in combination with hormonal methods associated with inhibition of ovulation. Women of non-childbearing potential may be included if they are either surgically sterile or have been

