1.5. Risks and Benefits for Study Subjects

In the Good Laboratory Practice repeat-dose toxicology studies consisting of up to 13 weeks of pexidartinib dosing, test article-related adverse effects were noted in testes (testicular spermatogonia reduction), ovaries (ovarian follicular degeneration), bone and bone marrow, hematology and lymphoid changes; these changes are consistent with the pharmacological mechanism of action of pexidartinib. All test article-related findings were partially or fully reversible.¹¹ Potential dose-related changes in bone marrow function can be monitored by peripheral cell count and differential counts. Because of the effects on reproductive organs, subjects will be monitored for changes in luteinizing hormone (LH), follicle-stimulating hormone (FSH), and other sex-specific hormone levels.

Effects on embryofetal development have been observed in both rat and rabbit toxicology studies up to 13 weeks. Dose level of 10 mg/kg/day was considered to be the NOAEL for embryofetal development when pexidartinib was administered orally by gavage to pregnant Sprague-Dawley rats. Dose of 20 mg/kg/day was considered to be the NOAEL for both reproduction in dams and embryo/fetal development. It was judged that pexidartinib was teratogenic in rabbits in the present study. Subjects in the study will be required to use adequate birth control during the study and for 90 days after the last dose of study treatment administered during study participation.

Findings in the nonclinical canine safety pharmacology study suggest that pexidartinib may have a negative inotropic effect. Subjects will be monitored for changes in ejection fraction with cardiac echocardiograms.

In clinical evaluation to date, the most common TEAEs of all grades have been fatigue, decreased appetite, nausea, vomiting, anemia, hair color depigmentation, and diarrhea. In a proportion of all subjects treated with pexidartinib, liver transaminases increased to approximately 1.5 × upper limit of normal (ULN) during the first cycle, followed by partial resolution during subsequent dosing. In some instances, the increase in liver enzymes may require dose hold or modification. Dosing modification guidance is included within the protocol for AE monitoring (Section 5.3). Liver function (clinical chemistry), renal function (clinical chemistry), and heart electrophysiology (QTc evaluation) will be monitored during this study.

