4.1.1. Inclusion Criteria

Each subject must meet all of the following criteria to qualify for enrollment:

1. Age \geq 18 years.
2. A diagnosis of PVNS or GCT-TS (i) that has been histologically confirmed either by a pathologist at the treating institution or a central pathologist, and (ii) where surgical resection would be associated with potentially worsening functional limitation or severe morbidity (locally advanced disease), with morbidity determined consensually by qualified personnel (eg, two surgeons or a multi-disciplinary tumor board).
3. Measurable disease as defined by RECIST 1.1 (except that a minimal size of 2 cm is required), assessed from MRI scans by a central radiologist.
4. Symptomatic disease because of active PVNS or GCT-TS, defined as one or more of the following:
 - a. a worst pain of at least 4 at any time during the week preceding the Screening Visit (based on scale of 0 to 10, with 10 representing “pain as bad as you can imagine”).
 - b. a worst stiffness of at least 4 at any time during the week preceding the Screening Visit (based on a scale of 0 to 10, with 10 representing “stiffness as bad as you can imagine”).
5. Stable prescription of analgesic regimen during the 2 weeks prior to randomization.
6. During the 2 weeks prior to randomization, at least 4 of 7 consecutive days of BPI Worst Pain NRS items and Worst Stiffness NRS items completed correctly.
7. Women of childbearing potential must have a negative serum pregnancy test within the 14-day period prior to randomization. (Where demanded by local regulations, this test may be required within 72 hours of randomization.)
8. Males and females of childbearing potential are permitted in the study so long as they consent to avoid getting their partner pregnant or becoming pregnant, respectively, by using a highly effective contraception method, as described below, throughout the study and for up to 90 days after completion. Highly effective methods of contraception

include: intra-uterine device (nonhormonal or hormonal), bilateral tubal occlusion, vasectomy, sexual abstinence, or barrier methods (e.g., condom, diaphragm) used in combination with hormonal methods associated with inhibition of ovulation. Women of non-childbearing potential may be included if they are either surgically sterile or have been postmenopausal for ≥ 1 year. Women who have documentation of at least 12 months of spontaneous amenorrhea and have an FSH level > 40 mIU/mL will be considered postmenopausal.

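### Section 5.4.2 advises contraception for 1 month after the last dose where Section 1.5 requires 90 days, and the methods accepted in criterion 8 do not match 5.4.2

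*Combined protocol and SAP*

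**What the plan says.** Three parts of the current protocol set out contraception rules.

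- **Section 5.4.2 (Hormonal Contraceptives).** For women who could become pregnant, the advice is an "effective, non-hormonal method of contraception during treatment with pexidartinib and for 1 month after the last dose". Men whose partners could become pregnant are likewise "advised to use an effective method of contraception during treatment with pexidartinib and for 1 month after the last dose". The pharmacological reason is that pexidartinib is described as a moderate CYP3A4 inducer, with a 57% fall in midazolam exposure, so that "there is a potential that exposure of ethinyl estradiol may decrease on concurrent administration with pexidartinib". Female partners of male subjects may use hormonal or non-hormonal methods.
- **Section 1.5 (Risks and Benefits).** Subjects will be "required to use adequate birth control during the study and for 90 days after the last dose of study treatment". The same section gives the animal finding: "It was judged that pexidartinib was teratogenic in rabbits in the present study".
- **Inclusion criterion 8 (synopsis and Section 4.1.1).** Subjects agree to highly effective contraception "throughout the study and for up to 90 days after completion". The accepted methods include an "intra-uterine device (nonhormonal or hormonal") and barrier methods "used in combination with hormonal methods associated with inhibition of ovulation". The others are bilateral tubal occlusion, vasectomy and abstinence.

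Section 9.4 separately asks for notification of pregnancies that begin during treatment or within 90 days of stopping it. It adds that reporting after the follow-up or early termination visit is voluntary.

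**The concern.** A site looking for contraception advice could reasonably open the section with that subject in its title, and there it finds 1 month. Another site, reading the risk section, finds 90 days. Each would be citing current text, and no passage in the supplied documents says which prevails.

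The method rules also diverge. A woman enrolled under criterion 8 with a barrier plus an ovulation-inhibiting hormone is using an option whose hormonal part Section 5.4.2 advises against. A woman who follows 5.4.2 with a barrier alone would not meet criterion 8.

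What is at stake is subject safety. The drug was judged teratogenic in rabbits, and 5.4.2 itself warns of possible embryo-fetal harm.

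**Working it through.** This is a comparison of texts with one subtraction. The plan gives no figure to reproduce.

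**Duration**

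| Place | Period after treatment | Counted from | Force |
|---|---|---|---|
| 5.4.2, both sexes | 1 month | last dose | advice |
| 1.5 | 90 days | last dose | requirement |
| Criterion 8 (synopsis, 4.1.1) | at most 90 days | completion | eligibility undertaking |

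Gap between 1.5 and 5.4.2 = 90 days minus 1 month.

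- Month of 31 days: 90 − 31 = 59 days, and 59/90 = 65.6% of the 90-day period.
- Month of 28 days: 90 − 28 = 62 days, and 62/90 = 68.9%.

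Criterion 8 cannot be put on the same scale. It sets a ceiling where a minimum is needed, and it does not start from the last dose.

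**What follow-up adds**

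- The 28-day post-treatment visit (28 ± 7 days) falls 21 to 35 days after the last dose and includes a serum pregnancy test where applicable (Sections 15.2.17 and 15.3.16).
- The 12-week visit (84 ± 7 days) falls 77 to 91 days after the last dose, or earlier if new therapy starts. It also includes a pregnancy test where applicable (Sections 15.2.18 and 15.3.17).
- Not every subject has the 12-week visit. Those who leave with progression, enter the separate continuation protocol, or have surgery within 12 weeks of the last dose do not.

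For subjects who reach the 12-week visit on schedule, the part of criterion 8 that covers the whole study therefore already extends to about 77 to 91 days after the last dose. The pregnancy tests would detect a conception in the gap but would not prevent one.

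**Method, female subjects only**

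| Method in criterion 8 | Consistent with 5.4.2? |
|---|---|
| Non-hormonal IUD, tubal occlusion, vasectomy, abstinence | Yes |
| Barrier plus ovulation-inhibiting hormone | No: the combination requires a hormonal method |
| Hormonal IUD | Not on the wording, but the stated rationale names only ethinyl estradiol |

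The barrier-plus-hormone option is the clearer mismatch. For male subjects there is no method conflict, because 5.4.2 lets their partners use hormonal methods.

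**Likely origin.** The top-line list of version 10.0 changes names 5.4.2 as updated and does not name 1.5 or 4.1.1. The list is not itself an error. The disagreement lies between sections of the current text.

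**The case against.** The strongest reply is that nothing here is irreconcilable. Section 1.5 requires and Section 5.4.2 only advises, and advice in a concomitant-medication section does not shorten a requirement. A subject who uses contraception for 90 days has also used it for 1 month. Four of the methods in criterion 8 satisfy both texts. This stands: nobody is forced to breach one section in order to obey another, and on a fair reading 90 days prevails. What remains is that no supplied passage tells sites to take the stricter rule.

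A second reply is that 5.4.2 was updated in version 10.0, so 1 month may be the sponsor's latest position. A reader might infer that it has replaced the 90 days. The documents do not say so: 1.5 is current text and still states a requirement. Nor do they show which period is pharmacologically right, so the proposed 90 days is the cautious default and should give way to a documented justification.

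Two further inferences should be resisted.

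- From the ceiling in criterion 8, a reader might conclude that subjects could stop contraception at the last dose. The undertaking also covers the whole study, which for many subjects runs to 12 weeks after the last dose.
- From Section 9.4, a reader might conclude that 90 days is the governing contraception period. That section is a notification rule, reporting under it becomes voluntary after the follow-up visit, and it sets no contraception period.

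**Conclusion.** The inconsistency is real and should be corrected. Its size is 59 to 62 days of post-treatment contraception that Section 1.5 requires and Section 5.4.2 does not mention, assuming a month of 28 to 31 days. Alongside it, criterion 8 accepts one method for women that plainly depends on hormones 5.4.2 advises against, and a hormonal IUD whose status is unclear.

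The exposure is a site that counsels from 5.4.2 alone. Post-treatment visits with pregnancy tests reduce it in part.

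A reader might go further and infer that subjects were wrongly counselled or harmed. The documents cannot support that. The consent pages are not in the copy reviewed, and the number of women using either hormonal option is not given. Confidence is high for the mismatch in the text and does not extend to its practical consequence. Sample size, type I error, power and the efficacy analyses are untouched.

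**What to change.** 1. In the synopsis, Section 4.1.1 criterion 8, Section 1.5 and Section 5.4.2, state one period for both sexes: during treatment and for at least 90 days after the last dose. If the sponsor prefers a shorter period, it should document the justification and use that period in all four places.
2. In criterion 8 (synopsis and 4.1.1), for female subjects, remove the option that depends on ovulation-inhibiting hormones. Either remove the hormonal IUD or state an explicit exception for it in 5.4.2.
3. Keep the 5.4.2 wording that lets female partners of male subjects use hormonal or non-hormonal methods.
4. Carry the agreed rule into the consent form.

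The cost is wording in four places and a consent update. Some women may need to change method. No endpoint, power calculation or analysis changes.
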